9.7.6. Patient-Reported and Health Economic Outcomes

Summary statistics over time, as well as changes from baseline over time, will be presented for the following outcome measures:

- MSIS-29 physical and psychological MS impact scores
- EQ-5D-5L index score, as well as 5 individual component scores
- EQ VAS (0-100 scale)
- MFIS-5 total score
- WPAI-MS impairment percentages
- Healthcare resource consumption (including number of hospitalizations [MS-related, non-MS related, relapse-related, resulting in steroid use], MS-related emergency room visits, MS-related neurologist visits, visits to other health care professionals for MS-related and other reasons) will be summarized over time with frequency distribution and/or descriptive statistics.

CONFIDENTIAL

The information contained herein may not be used, disclosed, or published without the written consent of Biogen Idec MA Inc.

9.7.8. Interim Analyses

Safety data will first be analyzed after 1000 patients have completed 6 months of follow up, then at least annually. Other study objectives may be assessed on a similar schedule.

9.8. Quality Control

9.8.1. Study Site Initiation

The Prescribing Physician must not enroll any patients in this observational study prior to completion of a study initiation visit, conducted by Biogen Idec or designee. This initiation visit will include a detailed review of the protocol and study procedures.

9.8.2. Quality Assurance

During and/or after completion of the study, quality assurance officers named by Biogen Idec or the regulatory authorities may wish to perform on-site audits. The physician will be expected to cooperate with any audit and to provide assistance and documentation (including source data) as requested.

9.8.3. Monitoring of the Study

Biogen Idec or designee representatives may conduct onsite visits at the study facilities for the purpose of monitoring various aspects of the study. The physician must agree to Sponsor-authorized personnel having direct access to the patient (or associated) files for the purpose of verifying entries made in the CRF, and assist with their activities, if requested. Adequate time and space for monitoring visits should be made available by the physicians or study staff. The site must complete the CRFs in a timely manner and on an ongoing basis to allow regular review by the study team.

9.8.4. Retention of Study Data

The minimum retention time for study records will meet the strictest standard applicable to that site, as dictated by any institutional requirements or local laws or regulations. Prior to proceeding with destruction of records, the physician is requested to notify Biogen Idec in writing. In addition, the physician is requested to notify Biogen Idec of any changes in the archival arrangements (e.g., archival at an off-site facility or transfer of ownership if the physician leaves the site).

9.9. Limitations of the Research Methods

Disease-specific background rates are important in populations like MS where the prevalence of confounding factors is likely different from the general population (e.g. immunosuppressant use). Background rates will be obtained from external databases due to reasons previously described in Section 9.2.2, such as potential channeling biases.

CONFIDENTIAL

The information contained herein may not be used, disclosed, or published without the written consent of Biogen Idec MA Inc.

However, the potential limitations of external databases, namely the differential ascertainment of select variables, should be acknowledged.

There is the potential for differential ascertainment of non-MS medication and over the counter (OTC) medications use. In this study, medication use will be documented by the Prescribing Physician. It is assumed that almost all Prescribing Physicians will be the patient's treating neurologist; therefore, capture of MS treatments should be fairly complete. Capture of other medications will depend on the patient's ability to accurately report concomitant medications to their neurologist. Medical claims databases capture prescription drug treatments when claims are submitted for reimbursement; they do not capture medications such as OTC medications which are not submitted for reimbursement. For the purposes of safety signaling, any bias attributable to unmeasured OTC medication use should not threaten the validity of safety signal analyses. The one exception may be OTC non-steroidal anti-inflammatory drugs (NSAID) and paracetamol use when evaluating renal and hepatic events, respectively. The potential for differential use of these agents should be considered when evaluating renal and hepatic event rates across data sources.

There is also the potential for differential ascertainment of medical events. The ascertainment of serious medical events will likely be similar in the proposed data sources. Also, ascertainment of malignancies and opportunistic infections should be similar, regardless of seriousness. A medical claim or patient record should be generated anytime a patient is diagnosed with a malignancy. Similarly, most patients with a clinically significant opportunistic infection will seek medical care; therefore, external databases should also provide reasonable background rates for these events. A differential ascertainment of these events between MS patients in the observational study and external databases is unlikely, so comparing these rates across the data sources should be appropriate. However, the availability of clinical details in external databases will likely be limited to information gleaned from medical terminology codes contained in a medical claim or electronic patient record.

The ascertainment of non-serious medical events may be more limited in external databases, particularly medical claims databases. Patients may not seek care for non-serious events (e.g. nasopharyngitis), therefore, these events would not be captured in external databases. The availability and validity of background rates for non-serious AEs leading to discontinuation will need to be evaluated on a case-by-case basis as they are reported. However, it may be appropriate to use data from the DMF clinical development program to calculate background rates for some non-serious events leading to discontinuation. For example, non-serious flushing and GI tolerability issues were routinely captured in the DMF clinical development program. The differences between the clinical trial population and the post-market population would need to be taken into account when making such comparisons.

The ascertainment of potential confounders, such as diabetes and hypertension, from a patient's medical history is subject to the limitations described above. For example, untreated diabetes or hypertension may not be well captured if the patient is not seeking medical care for these conditions. In addition, information on vital signs and lifestyle

CONFIDENTIAL

The information contained herein may not be used, disclosed, or published without the written consent of Biogen Idec MA Inc.

risk factors such as nicotine use are generally not available in most external databases. The limitations of these databases to identify confounders are widely acknowledged; however, medical and pharmacy records/claims are routinely used for confounding adjustment in pharmacoepidemiologic studies. The potential impact of residual confounding resulting from unmeasured comorbidities or medication use will be evaluated and noted for each comparison made with external databases, but it should not threaten the validity of these comparisons for purposes of signal detection.

Overall, any comparison of data from the observational study to external databases will be discussed in the context of its limitations.

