9.2.1.3.4. Lost to Follow-Up

If a patient has not been in contact with the Prescribing Physician for 12 months following his or her last routine visit, the site will contact the patient by telephone to assess the patient's interest in continuing study participation. If the site is unable to make contact with the patient, a follow-up attempt must be made. A site may consider a patient lost to follow-up after 3 failed documented contact attempts, one of which must be a certified letter. If a patient's status is determined to be lost to follow-up, this must be recorded on the End of Study CRF. If the physician ascertains a patient has died, the death should be recorded and reported as described in Section 11.2.4.1.

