9.3.2. Information Collected During the Follow-Up Period

The following information will be collected (unless otherwise noted) by the Prescribing Physician at each routine clinical practice visit, and also recorded. Visits are anticipated to occur approximately every 6 months. See also the Schedule of Events (Section 16.1).

- SAEs, including but not limited to infections (including opportunistic infections), hepatic events, malignancies, and renal events (note: all opportunistic infections and malignancies are to be reported as SAEs);
- AEs (including laboratory abnormalities) leading to treatment discontinuation;
- concomitant use of immunomodulatory, immunosuppressive (including corticosteroids), and anti-neoplastic agents, and other approved MS therapies (if any)
- concomitant use of hepatotoxic and nephrotoxic agents (e.g., paracetamol, nonsteroidal anti-inflammatory drugs, antibiotics, anticonvulsants, protease inhibitors, diuretics, and lithium) (if any)
- complete blood count (CBC) with differential, *if consistent with local regulations*††
- results of other clinical laboratory test results recommended in the local label (e.g., liver and renal function tests, urinalysis) *if consistent with local regulations*††
- recording of EDSS information (including Functional System Scores and Ambulation scores), based on neurological examination, *when collected as part of routine clinical practice* (i.e., not specifically performed for the study) †††
- recording of MS relapse information (see below for the definition of relapse)
- DMF prescription and utilization information, including prescribed dosing frequency, duration of DMF use, and primary reason for discontinuation of DMF

CONFIDENTIAL

The information contained herein may not be used, disclosed, or published without the written consent of Biogen Idec MA Inc.

- patient assessment of the following outcome measures, *if consistent with local regulations*: MSIS-29, EQ-5D and EQ VAS, MFIS-5, WPAI-MS, and healthcare resource consumption (as described above)††††
- pregnancy status (patient-reported, female patients) †††††

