11.1.2. Serious Adverse Event

An SAE is any untoward medical occurrence that at any dose:

- results in death
- in the view of the Prescribing Physician, places the patient at immediate risk of death (a life-threatening event); however, this does not include an event that, had it occurred in a more severe form, might have caused death
- requires inpatient hospitalization or prolongation of existing hospitalization
- results in persistent or significant disability/incapacity, or
- results in a congenital anomaly/birth defect.

While MS relapses resulting in hospitalization are considered SAEs, they will not be reported as SAEs in the study unless, in the opinion of the physician, a relapse is complicated by other SAEs.

All opportunistic infections and malignancies should be considered serious and reported as SAEs.

An SAE may also be any other medically important event that, in the opinion of the Prescribing Physician, may jeopardize the patient or may require intervention to prevent one of the other outcomes listed in the definition above. (Examples of such medical events include allergic bronchospasm requiring intensive treatment in an emergency room or convulsions occurring at home that do not require an inpatient hospitalization.)

CONFIDENTIAL

The information contained herein may not be used, disclosed, or published without the written consent of Biogen Idec MA Inc.

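### Section 9.9 assumes serious events are captured equally in the study and in external databases but argues only the external side; non-neurological SAEs may be under-captured, and the hospitalisation data already collected could check this cheaply

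*Protocol*

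**What the plan says.** On how SAEs enter the study, section 9.3.2 says: "The following information will be collected (unless otherwise noted) by the Prescribing Physician at each routine clinical practice visit, and also recorded". It adds: "Visits are anticipated to occur approximately every 6 months". Section 11.5 has the same physician complete the SAE form. Section 9.9 describes who that physician is: "It is assumed that almost all Prescribing Physicians will be the patient's treating neurologist".

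On what this reporter can know, section 9.9 says of non-MS drugs: "Capture of other medications will depend on the patient's ability to accurately report concomitant medications to their neurologist". A few lines later, on serious events, it says: "The ascertainment of serious medical events will likely be similar in the proposed data sources". It goes on to treat a difference in capture of malignancies and opportunistic infections as unlikely.

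On the comparison this supports, section 9.1 excludes an internal control cohort. Section 9.2.2 justifies claims and medical-record background rates on the ground that most SAEs involve hospitalisation. Section 9.7.3 reads potential signals from point estimates and 95% confidence intervals set beside those rates.

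On a second source, section 9.7.6 summarises healthcare resource use, including "number of hospitalizations [MS-related, non-MS related, relapse-related, resulting in steroid use". Section 9.2.1.2 counts all health-economic assessments among the patient-reported outcomes, and section 9.3.2 lets patients or a proxy complete them outside the clinic. Among the SAE criteria in section 11.1.2 is an event that "requires inpatient hospitalization or prolongation of existing hospitalization". The protocol does not link the two streams.

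**The concern.** Section 9.9 accepts that a neurologist's knowledge of non-MS drugs is limited by what the patient reports. An admission for pneumonia, hepatitis or renal failure under another specialty can be subject to the same limit, yet the section does not carry the reasoning over. Its support for similar ascertainment is that a diagnosis generates a claim or record and that patients with a significant opportunistic infection seek care. Both show that the external source holds the event. Neither shows that the study hears of it.

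The primary endpoint is the incidence and incidence rate of SAEs and of AEs leading to discontinuation, and the SAE rates are read against external sources. If the study alone misses events, the observed ratio to background is too low. That is the unsafe direction for a post-authorisation safety study, because it can look like reassurance.

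**Working it through.** **Inputs, from section 9.5 and Table 4.** n = 5000; exact binomial test, two-sided 0.05. Background p0 and risk ratio RR: malignancies 449.9 per 100,000 and 2.0; serious infections 2000 and 1.5; serious hepatic events 130 and 2.5; serious renal events 260 and 2.0.

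**Assumed input.** s = capture of serious events in the study relative to the background source. The protocol gives no value. Table 4 implicitly uses s = 1, so a range is shown.

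**Step 1: reproduce Table 4.** Take r as the smallest count with P(X ≥ r | 5000, p0) ≤ 0.025; power is P(X ≥ r | 5000, RR × p0).

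| Outcome | Expected count, 5000 × p0 | r | Power | Table 4 |
|---|---|---|---|---|
| Malignancies | 22.5 | 33 | 97.4% | 97% |
| Serious infections | 100 | 121 | 99.4% | 99% |
| Serious hepatic events | 6.5 | 13 | 82.3% | 82% |
| Serious renal events | 13 | 21 | 86.2% | 86% |

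The arithmetic of Table 4 is right, given equal capture.

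**Step 2: relax equal capture.** Keep r and replace RR × p0 by s × RR × p0.

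| s (assumed) | Malignancies | Infections | Hepatic | Renal |
|---|---|---|---|---|
| 1.00 | 97% | 99% | 82% | 86% |
| 0.95 | 95% | 97% | 77% | 80% |
| 0.90 | 90% | 90% | 70% | 72% |
| 0.80 | 71% | 48% | 54% | 51% |
| 0.70 | 42% | 7% | 35% | 29% |

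**Step 3: effect on the observed ratio.** The observed ratio is s × RR. For infections, a true 1.5 reads as 0.9 × 1.5 = 1.35, 0.8 × 1.5 = 1.20, or 0.7 × 1.5 = 1.05.

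**Step 4: false reassurance.** With no true effect and s = 0.8, the expected infection count is 0.8 × 100 = 80. The lower critical count is also 80, so the study would fall significantly below background with probability 53%.

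**Step 5: rare events.** The chance of at least one event is 1 − (1 − s × p)^5000. For p = 0.06% it is 95% at s = 1, as section 9.5 states, and 91% at s = 0.8. Detecting a single rare event is much less sensitive to capture than the comparison of rates.

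**What the figures cannot show.** The infection, hepatic and renal backgrounds in Table 4 come from trial placebo arms, and only the malignancy rate comes from a population registry. Section 9.7.3 plans no formal inferential comparison. The tables show how sensitive a rate comparison of this size is to s; they do not estimate bias in the planned claims or record-based comparisons. A common s for all four outcomes is a simplification.

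**The case against.** The strongest reply is that bias is nowhere demonstrated. A reader might infer that study SAE rates are biased low and signals are masked. The documents do not support that: no capture rate is stated, and the net direction is open. The study counts medically important events without admission, all opportunistic infections and all malignancies (11.1.2), and spontaneous abortions (11.4.2). These can raise study counts above hospital-based background rates. This objection stands, and it limits the point to possible under-capture.

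A reader might also infer that every non-MS admission without an SAE form is a missed SAE. It is not: section 11.1.2 requires an untoward medical occurrence. The share of reported admissions with a form is therefore not a measured capture rate. The questionnaire is itself patient- or proxy-completed, and the protocol states only a number of hospitalisations, without dates or diagnoses.

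Section 9.2.1.3.4 might suggest that patients on treatment are left for a year, since the site telephones "If a patient has not been in contact with the Prescribing Physician for 12 months following his or her last routine visit". That is the lost-to-follow-up procedure. Section 9.2.1.2 has the coordinating center chase the site when six-month data are missing, and a long gap may only delay a report. SAEs are also not said to come from patient recall alone: section 11.5 requires all SAEs to be recorded and followed up, and section 9.8.3 allows CRF entries to be checked against patient files. Those files show only what the site already knows, however.

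Section 9.9 does name possible differential ascertainment, hedges with a likelihood, and promises that comparisons will be discussed with their limitations. Section 9.2.2 adds that visit frequency should not differ from that under other first-line drugs. That bears on whether an event is diagnosed, not on whether the study is told.

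Finally, reconciliation may sit in data-management documents not shown. Its absence can be stated only of this protocol. The unsupported sentence in 9.9 is in this protocol.

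**Conclusion.** The point holds in a limited form. Section 9.9 assumes similar ascertainment of serious events, supports it from the external side only, and does not apply its own reasoning about medications to serious events treated outside neurology. Such events may be under-captured; if so, study rates are pulled down relative to claims or record-based rates. Neither the size nor the net direction can be derived from the documents.

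The stakes depend on s, which is assumed throughout. A 10% relative shortfall costs modest power for malignancies and infections and 12 to 14 points for hepatic and renal events. A 20% shortfall brings infections, hepatic and renal events to around one chance in two. Table 4 itself is not wrong. This is an inexpensive improvement worth making for a primary safety endpoint, not evidence that the study's rates are invalid.

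**What to change.** 1. In sections 9.6 and 11.2.2, let each non-MS hospitalisation reported on the healthcare resource questionnaire, during DMF use or within 30 days after the last dose and with no matching SAE form, trigger a site query. The query establishes date and reason where the questionnaire gives only a count. Record an SAE only if the site confirms an untoward medical occurrence meeting section 11.1.2.

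2. After the queries are resolved, report the share of confirmed SAE hospitalisations that had no SAE form before the query. Present it as a partial indicator of under-capture, not as a measured capture rate, and note that it rests on patient or proxy report and exists only where local rules permit the questionnaires.

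3. Replace the sentence on similar ascertainment in section 9.9. Say that study capture of non-neurological serious events may be lower, that this would bias study rates downward, and that external comparisons will be read with that in mind.

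Cost: a reconciliation listing, extra site queries, and the work of establishing dates and reasons. No added patients or visits are needed. Coverage will be incomplete.

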9.10. Other Aspects

9.10.1. Study Funding

Biogen Idec is the Sponsor of the study and is funding the study. All financial details are provided in the separate contracts between the institution, physician, and Biogen Idec.

9.10.2. Publications

Details on any restrictions on the publication of study data by Prescribing Physicians are included in the clinical study agreement for this study.

CONFIDENTIAL

The information contained herein may not be used, disclosed, or published without the written consent of Biogen Idec MA Inc.

10. PROTECTION OF HUMAN SUBJECTS

Biogen Idec and participating physicians must comply with this protocol and applicable International Conference on Harmonisation and Good Pharmacovigilance Practices guidelines, and conduct the study according to local regulations. The patient's privacy; physical, mental, and social integrity; and the confidentiality of his or her personal information will be strictly respected in accordance with the World Medical Association Declaration of Helsinki.

10.1. Ethics Committee

Participating physicians must obtain ethics committee approval of the protocol, informed consent form (ICF), and other required study documents prior to starting the study. The CRO (Section 3) will submit documents on behalf of the study sites in countries other than the US.

If the physician makes any changes to the ICF, Biogen Idec must approve the changes before the ICF is submitted to the ethics committee. A copy of the approved ICF must be provided to Biogen Idec. After approval, the ICF must not be altered without the agreement of the relevant ethics committee and Biogen Idec.

It is the responsibility of the physicians to ensure that all aspects of institutional review are conducted in accordance with current governmental regulations.

Biogen Idec must receive a letter documenting ethics committee approval, which specifically identifies the protocol, protocol number, and ICF, prior to the initiation of the study. Protocol amendments will be subject to the same requirements as the original protocol.

A progress report must be submitted to the ethics committee at required intervals and not less than annually.

At the completion or termination of the study, the study site must submit a close-out letter to the ethics committee and Biogen Idec.

10.2. Subject Information and Consent

Prior to any data collection under this protocol, written informed consent with the approved ICF must be obtained from the patient or patient's legally authorized representative, as applicable, in accordance with local practice and regulations. Written informed consent must be obtained from all patients participating in a clinical study conducted by Biogen Idec. [REDACTED]

Information about the DMF observational study and that study participation is voluntary for the patient must be explained to the patient. The patient must be given sufficient time to consider whether to participate in the study. A copy of the ICF, signed and dated by the patient, must be given to the patient. Confirmation of a patient's informed consent

CONFIDENTIAL

The information contained herein may not be used, disclosed, or published without the written consent of Biogen Idec MA Inc.

must be documented in the patient's medical record prior to any data collection under this protocol.

Each consent form should contain an authorization allowing the physician and Biogen Idec to use and disclose protected health information (i.e., patient-identifiable health information) in compliance with local law.

The signed consent form will be retained with the study records.

